8.7 Referrals

We will follow standard of care (MOH 2002) to refer participants for HIV/STI screening and care at the site. This care is not part of the study.

8.8 Contact tracing

Study staff will attempt to trace participants – using contact information provided by the participant for this purpose – if participants do not return for their Follow-up Visits in a timely manner.

8.9 Early study discontinuation

Participants have the right to withdraw their participation from the study at any time for any reason. They may also be discontinued if the study staff determines that further participation would be detrimental to the participants' health or well-being. All incidences of study discontinuation will be documented on the Study Discontinuation Form.

[figure not shown]
9. STATISTICAL CONSIDERATIONS

9.1 Sample size

Sample size calculations are based on detecting a clinically relevant RR of PSA positivity between the intervention and control arms. Our primary outcome is PSA positivity at the three follow-up points for each participant. Sample size calculations are based on formulae for correlated binary response variables (Fitzmaurice 1995; Jung 2003), using specifically GEE to fit a log-binomial model (Rochon 1998; Dahmen 2004). We show calculations (Figure 1) based on significance level of 0.05 (two-sided test), power to detect the effect set at 80% and 90%, and probability of PSA positivity in the control arm of 0.15. While the frequency of PSA positivity observed in past research has ranged from 8-38% (Table 2), these studies

almost uniformly either studied populations with PSA positivity that could be expected to be higher (sex workers) or lower (syndromic STI patients or women in serodiscordant relationships) than in the proposed trial. Only two trials studied HIV-negative women who were not sex workers or syndromic STI patients; PSA positivity in these trials ranged from 0.22 to 0.25 (Minnis 2009). To be conservative in ensuring an adequate sample size, we reduced our expected frequency of positivity roughly by 1/3 to 0.15. We assume an exchangeable correlation structure (same correlation, rho, between any two observations on the same subject). Given that previous studies produced an estimated rho of approximately 0.23 (Anderson 2013; Hobbs 2009; Gallo 2007), we display sample sizes required for values of rho ranging from 0.15 to 0.3. We considered RRs from 0.5 to 0.6, meaning a reduction of PSA positivity from 15% in the control arm to between 7.5% and 9% in the intervention arm. Finally, we adjusted the sample

Figure 2. Samples sizes per arm at various levels of rho for powers of 0.8 and 0.9 to detect RR of 0.5 to 0.6*

**Alpha = 0.05, PSA positivity in control arm = 0.15, attrition = 0.1 of participants fail to return post-enrollment and 0.25 of the remainder miss one follow-up visit)*

Table 2. Frequency of observed PSA positivity, by study

Study	Location	Female population	PSA tests	PSA positivity	
				No.	(%)
Hobbs 2003	Bangladesh	Sex workers	402	154	(38.3)
Evans 2013	Cambodia	Sex workers	183 at month 6	42	(23.0)
			172 at month 9	42	(24.4)
			170 at month 12	33	(19.4)
Pépin 2006	Guinea, Togo, Ghana & Mali	Sex worker, syndromic STI patients	508	94	(18.5)
		Syndromic STI clinic patients	658	58	(8.8)
Aho 2010	Guinea	Sex workers	219	84	(38.4)
Anderson 2013	Jamaica	Syndromic STI patients	285 at day 0	24	(8.4)
			286 at day 6	29	(10.1)
Rattray [in press] ^a	Jamaica	HIV-negative, seeking contraception	414 at month 0	103	(24.9)
			401 at month 1	93	(23.2)
			389 at month 3	95	(24.4)
Gallo 2007	Kenya	Sex workers	194 at month 0	30	(15.5)
			183 at month 12	21	(11.8)
Mose 2013	Kenya	In a HIV-discordant relationship	124	3	(10.5)
Gallo 2006	Madagascar	Sex workers	332	126	(38.0)
Minnis 2009^a	Zimbabwe	Sexually-active, HIV-negative	910	196	(21.5)

^a*Two trials of HIV-negative women who were not sex workers or syndromic STI patients*

sizes to account for attrition. Specifically, we assumed that 10% would fail to return after enrollment and, among the 90% remaining in the study, the probability of missing a follow-up visit would be 25%.

Given these assumptions, 500 subjects split equally in two arms will provide us with adequate power (80% for all assumed ranges of values and 90% in many) to detect a clinically meaningful reduction in PSA positivity for most values of rho. For example, at the estimated rho of 0.23, this sample size yields 80% power to detect a RR of approximately 0.61 at alpha level of 0.05. Thus, a total sample of 500 women will ensure adequate power to detect a clinically meaningful change in the frequency of PSA positivity between the study arms.

9.2 Randomization

After having been determined to be eligible and having provided written consent for participation, couples will be randomized to one of the two study arms in roughly equal proportions. The Statistician will prepare the randomization program in REDCap before study initiation. The concealment of allocation process will be accomplished using the relevant function in the REDCap electronic data capture system.

her male partner, prior condom experience, past sexual partners, history of other contraceptive method use, alcohol or other drug use, and perceived risk of infection or pregnancy and degree of motivation to avoid these) (Wingood 2000). Secondary analyses will include 1) identifying correlates of self-reported recent semen exposure (dichotomous variable for any report of vaginal sex without condom use with study partner in the past 48 hours) and 2) assessing whether correlates of semen exposure differ according to the outcome measure (PSA positivity or self-report). To conduct the latter exploratory analysis, we will simultaneously fit models for the two outcomes using bivariate logistic regression (Fitzmaurice 1995). We will apply GEE with alternating logistic regression (Carey 1993), which directly models within-woman associations using pairwise odds ratios. This bivariate approach will allow us to directly test whether the two models differ rather than assume that a significant finding in one model but not the other would imply that the two outcomes differ in their risk factors.

10. DATA MANAGEMENT

Given the potential for low participant literacy, trained study staff will administer all study forms and questionnaires and will electronically record responses directly onto a laptop computer using REDCap software. REDCap, which is supported by the Center for Clinical and Translational Science (CCTS) at OSU, facilitates the transmittal of secure, encrypted and password-protected data. CCTS will prepare the data entry screens with built-in quality control checks. Entered data will be instantaneously uploaded behind the secure OSU firewall. The PI will monitor the data during the study to resolve any potential issues upon detection.

In the case of internet outage or other technical difficulties, study staff will record data onto paper forms using a pen. These data will be entered into REDCap when the internet access is restored. PSA test results will be sent from the UNC laboratory to the PI in an electronic spreadsheet. The Site Investigator and PI will review the data files on an ongoing basis for accuracy. To maintain participant confidentiality, only a coded PIN will identify all data collection forms (DCFs), reports, and other records. Participants' names will be stored separately in a locked file in a locked office at the study site. No reports will link individual names with person-level data. Unique PINs will be used to link participant-specific data. All records will be secured in a locked room, accessible only by trained study staff. All computer entry and networking programs will be done with coded numbers only. Electronic files will be password-protected, with access only by authorized study personnel. Clinical information will not be released without written permission of the participant, except as necessary for monitoring by OSU or its designee.

11. TRANSLATION

All study materials will be translated into Vietnamese. After translation into Vietnamese, the DCF, Enrollment Consent Form and Futura Max Information Sheet will be back translated into English to ensure linguistic equivalence between the two versions.

12. INCIDENTS AND INCIDENT REPORTING

12.1 Adverse events

Adverse events (AEs) are defined as any untoward health-related reaction, effect, toxicity, or abnormal laboratory result that a study participant experiences during the course of a study. Only new untoward health-related events or worsening of a baseline condition are considered AEs.

An *unexpected* AE is one whose specificity or severity is not listed in the CSD500 package insert. Expected AEs include headaches, faintness and nausea, loss of sensation, dizziness and skin irritation. Information on expected AEs will be recorded on study DCFs, but these events will not be reported to the relevant IRBs unless the event is also serious or is an unanticipated problem involving risks to subjects or others (UPIRTSO).

Study staff will record information on all AEs that are classified 1) as possibly, probably, or definitely related to study participation or 2) as serious.

An AE is considered *serious* if it is fatal or life-threatening, requires in-patient hospitalization or prolongation of an existing hospitalization, results in a persistent or significant disability or incapacity, is a congenital anomaly or birth defect, jeopardizes the participant or requires intervention to prevent one of the outcomes listed above, or any other event deemed serious by the investigator. Study personnel will report any AE to the Site Investigator, who will determine 1) its relatedness to study participation and 2) its seriousness.

All SAEs will be reported in an expedited manner by completing the Adverse Event Form within two working days of when the site identifies the SAE. If it is determined that the SAE is unanticipated and anything other than "not related" (i.e., possibly, probably or definitely related), then the Site Investigator and PI will coordinate the notification of the relevant IRBs.

Non-serious AEs will be recorded on DCFs but do not require expedited reporting unless they are classified as UPIRTSO. All AEs will be managed according to the standard of care for the clinical practice and the judgment of the on-site clinicians.

12.2 Reporting other incidents that are unanticipated problems involving risks to subjects or others (UPIRTSO) incidents

UPIRTSO are any events or information that were unexpected and indicate that research procedures caused harm to participants or others or indicate that participants or others are at increased risk of harm. An unanticipated problem may involve any aspect of the research study and could involve anyone including participants, research staff, or others not directly related to the study. AEs that are unexpected and related and protocol violations are specific examples of UPIRTSO. Not all AEs are UPIRTSO, and not all UPIRTSO are AEs.

Examples of other UPIRTSO include 1) a breach of confidentiality; 2) a change to the protocol taken without prior IRB review to eliminate an apparent immediate hazard to a research participant; 3) halting of the study by a sponsoring agency; and 4) a participant complaint that indicates unexpected risks or that cannot be resolved by the study team. Any possible UPIRTSO will be recorded on the appropriate log and report form. The Site Investigator or designee will decide whether the incident meets the definition of UPIRTSO and, thus, requires prompt reporting to the IRBs.

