2. STUDY SUMMARY

This randomized controlled trial will test whether promoting the novel condom CSD500 (Futura Medical Developments; Surrey, UK) for improved sexual pleasure results in couples having less unprotected vaginal sex – measured with a biological marker of recent semen exposure – compared to the promotion of a standard condom for disease and pregnancy prevention. CSD500 contains an erectogenic drug and was developed to improve sexual pleasure by increasing penile firmness, size, and erection duration.

We will recruit eligible, monogamous, heterosexual couples at Thanh Hoa Provincial Centre of Reproductive Health in Vietnam to participate in a randomized controlled trial (RCT) of two balanced arms of approximately 250 couples each. At enrollment and at three follow-up visits scheduled at 2, 4 and 6 months after enrollment, we will provide condom counseling, will collect double-headed vaginal swabs to test for the semen biomarker, prostate-specific antigen (PSA), and will administer a questionnaire to the female participants on their demographics, sexual and condom-related attitudes and practices, including sexual pleasure and perceptions of partner's sexual pleasure. Although the intervention is directed to the women, couples will be enrolled to ensure that the male partners consent to CSD500 use. After enrollment, male participants will not participate in study visit activities, including data collection, until the time of their female partner's final 6-month visit. Because of the differences in counseling messages, participants and study staff at the site cannot be blinded to arm assignment.

Primary aims:

1. To evaluate whether CSD500 provided to improve sexual pleasure, as compared to the standard condom, results in less semen exposure among women in an established relationship
2. To evaluate the effects of CSD500 provision on men and women's reports of sexual pleasure compared to the standard condom
3. To identify correlates of semen exposure measured by PSA positivity

Study design: RCT with two arms: CSD500 for sexual pleasure or the standard condom currently provided for pregnancy and disease prevention

Study site: Thanh Hoa Provincial Centre of Reproductive Health

Data collection: Women: questionnaires and vaginal swabs for PSA testing at enrollment and the 2, 4, and 6-month visits
Men: questionnaires at enrollment and the 6-month visit

Sample size: ~500 couples with balanced assignment to the two study arms

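### Section 12.1 gives conflicting rules on which non-serious adverse events are recorded, and one reading makes recording depend on a relatedness judgement by unblinded site staff

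*Combined protocol and SAP*

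**What the plan says.** Section 12.1 of the protocol contains three statements about recording.

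- Rule A: "Study staff will record information on all AEs that are classified 1) as possibly, probably, or definitely related to study participation", or as serious.
- Rule B: "Information on expected AEs will be recorded on study DCFs". The list that goes with it reads: "Expected AEs include headaches, faintness and nausea, loss of sensation, dizziness and skin irritation".
- Rule C: "Non-serious AEs will be recorded on DCFs but do not require expedited reporting unless they are classified as UPIRTSO".

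Rule A carries a relatedness condition for anything not serious. Rules B and C carry none, and none of the three mentions the arm. Whether an AE is expected is decided by comparison with the CSD500 package insert, and no separate definition is given for control couples.

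The same section has staff bring any AE to the Site Investigator, "who will determine 1) its relatedness to study participation and 2) its seriousness". The Study Summary (section 2) says that "participants and study staff at the site cannot be blinded to arm assignment". Section 9.3.1 keeps only the Statistician and laboratory staff masked. Section 13.8 has the DSMC review accumulated data and make safety recommendations by judgement, without specific stopping guidelines.

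**The concern.** A rule that records a non-serious event only after someone has called it related makes the record depend on that person's opinion. Here the person very probably knows the arm. The documents do not single out the Site Investigator on masking, but the role falls naturally under site study staff. An investigator who knows that a couple has a condom containing glyceryl trinitrate may be readier to call a headache related than one who knows that the couple has a plain condom. If so, the two arms' counts pass through different filters before anyone compares them.

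At stake is the background rate. A committee judging safety without numerical guidelines needs to know how often headache or dizziness occurs in control couples before it can read the count in CSD500 couples. If control events are dropped as unrelated, an excess can appear with no drug effect, or a real excess cannot be separated from background.

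**Working it through.** The plan states no AE rate, relatedness probability or AE test, so there is no figure to reproduce. The check has two parts.

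**1. The three rules side by side**

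| Type of AE | Rule A | Rule B | Rule C |
|---|---|---|---|
| Non-serious, listed symptom, judged related | recorded | recorded | recorded |
| Non-serious, listed symptom, judged unrelated | outside the rule | recorded | recorded |
| Non-serious, unlisted, judged related | recorded | silent | recorded |
| Non-serious, unlisted, judged unrelated | outside the rule | silent | recorded |
| Serious | recorded | recorded if expected | not addressed |

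The conflict lies in the second and fourth rows.

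Rule A does not contain the word *only*, so the rules could be harmonised by treating it as a minimum. But if Rule C covers every non-serious AE, and serious AEs are recorded anyway, everything is recorded and Rule A has no content. A site would therefore reasonably read Rule A as a restriction. Rules B and C sit in sentences mainly about what need not go to the IRBs or be expedited, so a site could also read them as operating inside Rule A. Three practices are compatible with the text:

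- Rule A governs: both conflicting rows are filtered by relatedness.
- Rules A and B govern: listed symptoms are recorded in both arms, and the filter touches only unlisted non-serious AEs.
- Rule C governs: there is no relatedness filter.

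**2. Illustration of the first practice (all rates and probabilities are assumptions)**

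Let p be the true rate of a non-serious event, equal in both arms. Let q1 (CSD500) and q0 (control) be the probabilities of being called related.

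- Recorded rate = p × q in each arm.
- Recorded risk ratio (RR) = (p × q1) / (p × q0) = q1 / q0, whatever p is.

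| q1 | q0 | Recorded RR |
|---|---|---|
| 0.5 | 0.5 | 1.0 |
| 0.6 | 0.4 | 1.5 |
| 0.8 | 0.2 | 4.0 |

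With p = 6% and the last pair, recorded rates are 6% × 0.8 = 4.8% and 6% × 0.2 = 1.2%. At about 250 couples per arm (section 2), counting one event at most per couple, that is 12 recorded events against 3, from 15 true events in each arm.

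Suppose someone tested such a difference, which the plan does not propose. The chance of two-sided p < 0.05 is approximately Φ[(d − 1.96 × se0) / se1], with d the difference in recorded rates, se0 the pooled and se1 the unpooled standard error. At p = 10% and 250 per arm:

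| q0 | q1 | Recorded, control | Recorded, CSD500 | RR | Chance of p < 0.05 |
|---|---|---|---|---|---|
| 0.5 | 0.8 | 5.0% | 8.0% | 1.60 | 27% |
| 0.3 | 0.8 | 3.0% | 8.0% | 2.67 | 69% |
| 0.2 | 0.9 | 2.0% | 9.0% | 4.50 | 93% |

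For the first row, d = 0.03, se0 = 0.02205 and se1 = 0.02201, so (0.03 − 0.0432) / 0.0220 = −0.60 and Φ(−0.60) = 0.27. Over true rates of 5% to 20%, these three pairs give about 16% to more than 99%. With q1 = q0 the chance is the nominal 5%.

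**The case against.** A reader might infer that non-serious AEs are recorded only when the unmasked investigator calls them related, so that side-effect rates cannot be compared. The documents do not support that.

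- Two of the three sentences require recording with no relatedness condition. One covers exactly the product's known effects, and on its face a control couple's headache is as much a listed AE as a CSD500 couple's.
- Relatedness is to study participation, not to the drug, and *possibly* is enough. The documents do not show how control events would be judged.
- The illustrative risk ratios restate the chosen probabilities and apply only if Rule A governs.
- Safety is not one of the three aims, and section 9.3 plans no between-arm AE comparison. Serious AEs are recorded whatever their cause.
- The questionnaires, the Adverse Event Form and the DSMC charter are listed as attachments, but their content was not available for this review. They may already ask both arms about the listed symptoms in the same words.

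All of this stands, and it limits the point. It does not remove it. Nothing in section 12.1 says which sentence prevails, and the one that most looks like a general rule is the restrictive one. The rest of the protocol does not settle it either: section 8.4 invites participants to return for problems they see as study-related, and the schedule of procedures marks the Adverse Event Form as completed only if needed at every visit.

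**Conclusion.** Section 12.1 contradicts itself on the recording of non-serious AEs judged unrelated, and the sentences need to be reconciled. The consequence is conditional. If the related-or-serious sentence is applied as a filter, and relatedness judgements differ by arm, AE counts seen by the DSMC and in any descriptive safety summary may not be comparable. If the expected-AE sentence is honoured alongside the filter, the problem shrinks to unlisted non-serious AEs. If the non-serious sentence governs, it disappears.

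The size cannot be derived from the documents. Under the stated assumptions the recorded risk ratio with no true effect runs from 1.0 (equal probabilities) through 1.5 to 4.0 or 4.5. The primary PSA analysis is not affected. The change is worth making because it is cheap and protects data that the DSMC assesses by judgement alone.

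**What to change.** Replace the three sentences in section 12.1 with one rule:

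- Delete the related-or-serious condition on recording.
- Record AEs in both arms regardless of relatedness. At minimum this must cover the listed symptoms: headache, faintness, nausea, loss of sensation, dizziness and skin irritation.
- Ask about those symptoms with identical wording in both arms. First check the follow-up questionnaires and the Adverse Event Form, which may already do this.
- Keep relatedness as a separate field, used for reporting decisions and not as a condition for entry.

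Reporting to the IRBs and expedited reporting can stay as written. The cost is a wording change in the protocol and possibly the forms, plus some additional minor AE entries.

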12.3 Sponsor and principal investigator responsibilities

The sponsors, PI, Site Investigator, or designees have the authority to stop the study due to SAEs, UPIRTSOs, protocol violations, or problems related to inadequate recruitment or follow-up, or upon the direction of an IRB.

The Site Investigator or designee has the authority to change the protocol to eliminate an apparent immediate hazard to a research participant.

13. PROTECTION OF HUMAN SUBJECTS

13.1 Informed consent process

Study staff will read the Annotated Enrollment Consent Form aloud to the couple. This Form is identical to the Enrollment Consent Form except that the former has questions embedded to ask to the potential participants to gauge their comprehension of the study during the consent process. Only couples who demonstrate comprehension of the answers to these questions will be enrolled.

Both members of the couple will indicate their agreement to participate in the study by signing the Enrollment Consent Form. Individuals who are illiterate will provide an "X" on the form to indicate consent; the full discussion of the consent process for these participants will be conducted in the presence of a witness, who will sign the Enrollment Consent Form indicating that the witness has observed the entire consent process. The female and male participants will be asked for their consent for future contact about new research. They will indicate whether they consent to this by checking the appropriate box on the Enrollment Consent Form. The couple do not consent to future contact, they can still enroll in the study. The couple will be given an unsigned copy of the Enrollment Consent Form to keep for future reference, as it provides contact information for staff responsible for the conduct of the research study in the event of any questions or concerns.

